1.0 Objectives / Specific Aims

Aim 1. Assess whether the parasympathetic effects of transcutaneous auricular vagus nerve stimulation (taVNS) are able to attenuate the sympathetic response curve elicited by a validated cold pressor test.

We will recruit 24 neurotypical subjects (ages 18-65) in order to have at least 14 completers. The subjects must be at baseline healthy, and not have a history of major mental or medical illness (see more below for full inclusion/exclusion criteria). Each subject will undergo phone screen and be consented prior to participating in the study. Each subject will participate in 1 study visit, where they will participate twice in the validated cold pressor test while concurrently receiving active or sham taVNS. Subjects will participate in both treatment conditions (active and sham taVNS), however the order in which they participate will be randomized (half will receive active taVNS first, half will receive sham first). The cold pressor test is a validated stress induction technique and has been shown to produce a reliable sympathetic response, as shown by acute elevations in sympathetic physiologic markers (heart rate, blood pressure/mean arterial pressure, cardiac output, etc). In prior studies, taVNS has been shown to produce a marked and significant parasympathetic response in neurotypical subjects, shown by acute reductions in the same markers as above. Both taVNS and the validated cold pressor test have been shown to be safe and feasible in neurotypical subjects. We hypothesize that subjects receiving active taVNS will have an attenuated sympathetic response to the cold pressor test compared to those receiving sham stimulation.

Aim 2. Assess whether taVNS affects the subjective pain/stress response to a validated cold pressor test.

Subjects will be asked to rate subjective pain and stress before, during, and after the cold pressor test. We hypothesize that these subjective ratings will be reduced in the group receiving active taVNS compared to the sham group.

Aim 3. Assess the acute effects of transcutaneous auricular vagus nerve stimulation (taVNS) on anxiety.

In other pilot trials using taVNS, as well as past trials with implanted VNS, results have shown taVNS and implanted VNS to have an anxiolytic effect. We hypothesize that taVNS will have a similar anxiolytic effect on subjects in this trial. This work will provide pilot data for subsequent studies to investigate the anxiolytic effects of taVNS.

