6.0 Number of Subjects

We will recruit 24 adults in order to have at least 14 completers.

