10.0 Study Design / Method

After completing the phone screener, participants will be invited to in-lab participation for 1 visit: they will be provided available times and instructed on how to locate the laboratory space. They will be asked to refrain from the following prior to the study: Tobacco use within 2 hours, Caffeine within 6 hours, Alcohol within 24 hours, and intense physical activity within 24 hours. Participants will be asked to sleep as they usually do the night before the study.

Prior to arrival to the research space, after phone screening, participants will be consented at the in-person visit (see Section 9.0). Subjects will present to the laboratory for 1 visit. Once participants have arrived in the laboratory for the visit, if they are a woman of childbearing age, they will be provided with a pregnancy test strip to take in privacy. They will be provided instructions on how to use the test, as well. After completing the pregnancy test, participants with negative results will be asked to continue to the remaining study procedures, whereas those with a positive result will be debriefed, compensated for their time, and released.

During the laboratory visit, subjects will twice participate in a validated stress induction technique known as the Cold Pressor Test (CPT) while concurrently receiving either active or sham transcutaneous auricular vagus nerve stimulation (taVNS). Over the course of 2 cold pressor tests, subjects will receive both stimulation conditions (half will be randomized to receive active stimulation first and half will receive sham stimulation first). Physiologic measures will be collected before, during, and after each CPT, and there will be a resting period of at least 25 minutes between each CPT. Subjective measures of anxiety, stress, and pain will also be collected throughout the procedure. See Figure 2 for a timeline of the study visit's course.

Figure 2. Study visit timeline (for participant randomized to receive active taVNS first)

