Timeline consists of 2 cold pressor tests (CPT) and 2 stimulation conditions (active and sham). The cold pressor test (CPT) will last for up to 3 minutes. Subjects will receive either active or sham taVNS for up to 5 minutes (stimulation will start prior to CPT and continue throughout the duration of the CPT). The order in which participants receive active or sham taVNS will be randomized, but all participants will receive both treatment conditions. Physiologic data will be continuously measured throughout the course of each visit.

Cold Pressor Test: The CPT was first introduced in the 1930s by Hines and Brown (Hines, 1932). CPT exposure leads to profound changes in cardiovascular parameters most notably a rise in blood pressure throughout peripheral vasoconstriction and to a lesser extent cardiac output resulting from an increase in both vascular alpha-adrenergic and cardiac beta-adrenergic drive (Greene et al., 1965; Lollo, 1975; Yamamoto et al., 1992). On the subjective level participants experience the CPT as painful and report heightened levels of perceived stress and arousal during and immediately after the water-bath (Zoladz et al., 2014). A plethora of research has contributed to the validation and standardization of the CPT.

Prior studies have shown an enhanced response, in terms of sympathetic parameters, to a bilateral feet CPT (Larra, 2015). This is what will be used in this trial. As in previous studies (Larra, 2015; Bachman, 2018), the CPT will consist of participants immersing both feet into ice-water (water temperature around 2-3 degrees Celsius) for up to 3 minutes. The water-bath will be a rectangular tub with ample volume to submerge the subject's feet completely with ice-water.

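### Do the group-worded hypotheses in Aims 1 and 2 commit this crossover trial to an unpaired analysis that ignores order?

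*Protocol*

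**What the plan says.** Protocol 1.0 states a directional hypothesis with a comparator for two of its three aims. For Aim 1 it is that "subjects receiving active taVNS will have an attenuated sympathetic response to the cold pressor test compared to those receiving sham stimulation". For Aim 2 it is that "these subjective ratings will be reduced in the group receiving active taVNS compared to the sham group".

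The design is a two-period crossover within one visit. The Aim 1 paragraph says so before it reaches its hypothesis: "Subjects will participate in both treatment conditions (active and sham taVNS), however the order in which they participate will be randomized". Section 10.0 repeats it twice: "half will be randomized to receive active stimulation first and half will receive sham stimulation first", and under the timeline, "The order in which participants receive active or sham taVNS will be randomized, but all participants will receive both treatment conditions". Section 3.0 says the same. On spacing, section 10.0 states that "there will be a resting period of at least 25 minutes between each CPT". On size, section 6.0 states: "We will recruit 24 adults in order to have at least 14 completers".

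The only text labelled as analysis, in section 12.0, concerns processing of the physiological signals. It names no statistical test, model or unit of analysis.

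**The concern.** The two hypotheses appear to name a contrast that the design cannot produce. Nobody belongs to an active group or a sham group; the only randomised groups are the two orders. An analyst who took Aim 2 at its word would compare active readings with sham readings as if they came from different people. That ignores the correlation between two readings on one person and gives up the main advantage of a crossover, in a trial that may finish with 14 people.

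A second worry concerns order. The same cold stressor is repeated after as little as 25 minutes, so the second response may differ from the first. A plain active-minus-sham difference that takes no account of period leaves that change in the error term. If losses make the two orders unequal, part of the change also enters the treatment estimate.

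**Working it through.** There is no protocol figure to reproduce: section 6.0 gives no power, alpha, effect size, SD or correlation. The check has two parts: what the text commits to, and how much would be lost if it were followed literally.

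**What the text commits to**

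- Aim 1 hypothesis: it compares subjects receiving one stimulation with those receiving the other. Groups are not mentioned, and in a crossover this is common shorthand for the two conditions.
- Aim 2 hypothesis: it does say group. This wording does not fit the design.
- Design statements in 1.0, 3.0 and 10.0: all agree that each participant has both conditions and that order is randomised half and half.
- Section 12.0: signal processing only.

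No sentence proposes an unpaired test, and none proposes a difference unadjusted for period.

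**Cost of ignoring the pairing**

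From the protocol: n = 14, the floor in section 6.0. Assumed: two-sided alpha 5%, equal SD σ in both conditions, within-subject correlation ρ of 0.3 to 0.6, and a true effect of 0.81 SD of the paired difference, which gives the paired t-test (13 df) 80% power.

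- Paired SE = σ√(2(1−ρ)/n); unpaired SE = σ√(2/n); ratio = 1/√(1−ρ).
- ρ = 0.3: 1/√0.7 = 1.20; ρ = 0.5: 1/√0.5 = 1.41; ρ = 0.6: 1/√0.4 = 1.58.
- Unpaired power by simulation: 71%, 56% and 44%.
- Actual type I error of the unpaired test: 2.1%, 0.8% and 0.4%, against a nominal 5%.

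The error is conservative: it loses power but does not create false positives.

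**Cost of ignoring period**

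Let the first-to-second change be π, in SDs of the paired difference. It adds π to the active-minus-sham difference in one order and subtracts it in the other. With 7 per order the shifts cancel in the mean but remain in the variance.

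- Plain paired power: 78% at π = 0.25, 72% at 0.5, 62% at 0.75.
- Period-adjusted power (12 df): 79% throughout.

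**Unequal orders**

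Assume 12 per order at entry and completion at random.

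- 14 completers: P(7/7) = C(12,7)²/C(24,14) = 792²/1,961,256 = 0.320; P(9/5 or more uneven) = 0.214.
- A 9/5 split shifts the unadjusted estimate by (9−5)/14 = 29% of π.
- Over all random splits the mean absolute shift is 13% of π, and the expected shift is zero.
- 20 completers: the most uneven possible split is 12/8, with probability 2 × C(12,8)/C(24,20) = 2 × 495/10,626 = 0.093.

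The arithmetic is sound, but each loss belongs to an analysis that appears nowhere in the protocol.

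**The case for a change.** The strongest case for acting is that this is a misstatement and not an omission. The protocol names a contrast, names it wrongly, and has no later analysis text to override it. Aim 1 carries the primary physiological outcomes. A paired analysis plan would, read strictly, depart from the protocol's own hypotheses. Correcting two sentences costs nothing, and adjusting for period costs one degree of freedom.

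Part of this stands. Aim 2's wording is inaccurate, and a paired analysis allowing for period is the natural one for this design.

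The rest does not. A hypothesis giving the direction of an effect does not specify an analysis, so a paired model would not depart from it in any way that matters. Aim 1 reads naturally as a comparison of conditions. The point about order has no text to attach to, and randomising the order half and half is already the design's protection against a period effect. The larger losses depend on the chosen inputs: at ρ = 0.3 unpaired power is 71%, and at π = 0.25 the plain paired test keeps 78%. The 9/5 split takes the floor of 14 and assumes that all ten losses come after randomisation. Yet the study is a single visit, and a positive pregnancy test ends participation before any stimulation, so some losses can come earlier.

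**Conclusion.** No change to the plan follows. One word in Aim 2 is loose, and Aim 1's phrasing is acceptable shorthand. The crossover is stated in the same section before either hypothesis and repeated elsewhere, so the intended contrast is clear and an analyst would take it within participants. Whether period and sequence enter the model is ordinarily settled in the statistical analysis plan; the protocol neither excludes them nor fixes anything against them.

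The effect on results is nil unless someone overrides the evident design. In that case the cost would be lost power (80% to between 71% and 44% for ρ from 0.3 to 0.6 at n = 14) with a type I error below nominal. Those figures rest on an assumed alpha, power and correlation, and the order figures on an assumed period effect and random completion. The protocol gives none of these, so they show scale and are not evidence of a flaw.

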2.0 Background

Improving treatment for anxiety and related conditions is essential, as anxiety disorders, for example, have a lifetime prevalence of 16.6% (Remes et al., 2016) and remission rates at only 51% after frontline exposure therapy (Springer et al., 2018). Enhancing acceptability and improving treatment refractory rates are *key*. Transcutaneous auricular vagus nerve stimulation (taVNS) is a brain stimulation candidate for disorders characterized by sympathetic hyper-activity (i.e., fight-or-flight; Badran et al., 2018c), including but not limited to generalized anxiety disorder, social anxiety disorder, panic disorder, and posttraumatic stress disorder. In fact, taVNS is thought to target transdiagnostic mechanisms, those mechanisms which are not diagnosis specific and cut across psychiatric illnesses. These include inflexible stress responses, heightened anxious arousal, and impaired cognitive processing (Deuchars et al., 2018). There are many advantages to taVNS over other stimulation technology, as it is non-invasive, affordable, and safe enough to implement at home or in the cognitive-behavioral therapy (CBT) clinical setting, without immediate MD oversight.

The vagus nerve is the longest cranial nerve and maintains parasympathetic control over the heart, lungs, and digestive track, while also providing the prefrontal cortex with somatic and visceral feedback (Porges, 2001). It contains a variety of fibers which provide sympathetic and parasympathetic innervation and carry somatic and visceral afferent and efferent information. Given the vagus nerve's contributions to cardiac functioning, it is often indexed using heart rate variability (HRV; beat-to-beat changes in the heart rate), also referred to as vagal tone. Pharmacological blockade of the vagus results in increased heart rate suggesting that cardiac activity is regulated by inhibitory vagal control. Chronic stress, on the other hand, leads to protracted sympathetic disinhibition, inflexible parasympathetic activity, and maladaptive cognitive responses. In fact, low vagal tone and poor inhibition of sympathetic activity (i.e., fight-or-flight) is implicated in a range of psychiatric conditions and mental health problems, including emotion regulation difficulties, anxiety, depression, and PTSD.

Preclinical and clinical trials show that implanted vagus nerve stimulation (VNS) may be an effective anxiolytic treatment and may improve outcomes in anxiety disorders. In order to develop therapeutic taVNS for psychiatric problems, investigating the effects of taVNS during a stress induction technique would be a logical first step. The cold pressor test (CPT) is a valid and reliable test that allows us to elicit a sympathetic stress response in neurotypical subjects in a safe and monitored environment. The CPT was first introduced in the 1930s by Hines and Brown (Hines, 1932). CPT exposure leads to profound changes in cardiovascular parameters most notably a rise in blood pressure through peripheral vasoconstriction and to a lesser extend cardiac output resulting from an increase in both vascular alpha-adrenergic and cardiac beta-adrenergic drive (Greene et al., 1965; Lovallo, 1975; Yamamoto et al., 1992). The CPT will also allow us to investigate if the parasympathetic actions of taVNS are able to attenuate the typical sympathetic response of the CPT. To date, there have not been any similar studies looking at the effects of taVNS on a provoked sympathetic stress response.

3.0 Intervention to be studied

The intervention we are studying is called transcutaneous auricular vagus nerve stimulation (taVNS). taVNS is simply electrical nerve stimulation administered at the ear which targets the auricular branch of the vagus nerve. taVNS will be administered using the Digitimer DS7a nerve stimulation system that has an FDA 510k approval. taVNS is a non-significant risk method that has been approved by the MUSC IRB for many ongoing taVNS trials.

The Digitimer DS7a manual has been uploaded the MUSC IRB portal and can be found here: <https://www.digitimer.com/product/human-neurophysiology/peripheral-stimulators/ds7a-ds7ah-hv-current-stimulator/>

- Cervical VNS is FDA approved for medication resistant epilepsy as well as medication resistant depression (Livanova). FDA pivotal trials are underway for paired cervical VNS with rehab for stroke (microtransponder). Noninvasive cervical VNS is FDA approved for treating cluster headache (electrocore). To date there are no FDA approved indications for taVNS.
- We will use the device during each study visit for up to 5 minutes while subjects concurrently participate in the cold pressor test. Subjects will receive both stimulation conditions over the course of the study visit (active taVNS x1, sham taVNS x1). Subjects will be blinded to stimulation condition, but the research team will know whether patients are receiving active or sham stimulation. The order in which subjects receive either active or sham stimulation will be randomized (half will receive active taVNS first, half will receive sham taVNS first).

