7.0 Setting

All participants will complete the study tasks in a dedicated research suite, the Psychophysiology Center, in the Brain Sciences Department. The space to be used here is currently assigned to researchers on this study team and is well equipped for stimulus-controlled physiological recording. In addition, this space is used only for research protocols and thus is accessed at limited times. Studies assigned to this space may only enter during their assigned hours to ensure participant confidentiality and privacy. This also ensures COVID-19 related precautions may be taken: limiting use of space to no more than the participant and the study researcher and allowing time between participants for cleaning/sanitation, requiring the use of masks for researchers and participants.

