Upon arrival, subjects will be asked to sit comfortably in a chair as electrodes are applied to collect physiological data (see physiology section below). The protocol will start with a resting period during which heart rate and blood pressure will be assessed. Subjects will receive a 2-minute warning prior to the start of the CPT. Subjects will be asked to rate subjective anxiety, stress, and pain during this resting period. After the resting period, subjects will be exposed to the CPT for up to 3 minutes. During the exposure to the ice water, subjects will again rate subjective anxiety, stress, and pain. The stress procedure will be followed by another resting period, during which heart rate and blood pressure will continue to be monitored. Again, participants will rate subjective anxiety, stress, and pain.

taVNS: The taVNS stimulation administered during the study *is non-invasive but includes some risk*. Participants will be screened for potential contraindications to taVNS prior to invitation to the lab (see Section 5.0 for exclusion criteria; e.g., ear trauma/pain, metal implants). The device has safety mechanisms to prevent electrical surges. Skin will be prepared using 70% alcohol swabs prior to electrode attachment to ensure sanitation and stimulation power is safe. Metal jewelry also will be removed from the head. Stimulation is applied using electrodes and a water based conductive gel, and participants will be assessed after application/prior to stimulation for discomfort related to the electrode. Participants will be assessed during stimulation for discomfort or adverse events over the course of stimulation, though

studies have demonstrated few concerns of safety. Participants are encouraged to share report of discomfort and are reminded prior to the study they may discontinue at any point. The ear also will be cleaned and inspected for irritation/redness after stimulation. The ear stimulation delivered during the study includes some risk. Participants in previous research using this stimulation describe the feeling as a “tickle” or “pricking” sensation. Some report mild irritation. Our researchers will inspect the ear after stimulation given previous research has documented some redness from the stimulation.

Physiology: For sensors that are attached to skin there is some risk for mild local irritation or redness, thus adhesives are removed with caution/gently.

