12.0 Data Management

Analyses: The psychophysiological data will be processed using standard protocols which have previously been used in this lab and in various other studies (Sege et al., 2017, 2018, Taylor et al., 2020), and according to published guidelines (Blumenthal et al., 2005; Boucsein et al., 2012; Gatchel et al., 1973; Keil et al., 2014).

Telephone screening information will be stored in a locked filing cabinet in the Brain Stimulation Lab, along with each participant’s signed informed consent. Data regarding subject’s ratings of subjective anxiety/stress/pain will be stored in the Redcap database. Information about the participant (including their identifiable private information and/or any identifiable biospecimens) may have all of their identifiers removed and used for future research studies or distributed to other researchers for future research without additional informed consent from them or their legally authorized representative.

Confidentiality and Quality Control: All study personnel will complete Social-Behavioral-Educational research CITI training, and also complete in-lab training regarding data security practices. Study personnel will be trained in the IRB protocol. The investigator, and co-investigators will be available to monitor data collection to ensure quality, confidentiality, and adherence to the IRB protocol.

The majority of this study’s procedures will take place in the study’s research suite, which is a private room with limited access. Regarding documentation, participant names will appear only on the IRB-approved Consent, HIPAA, and payment forms. It cannot be guaranteed that participants will complete these study portions in private spaces, though they will be encouraged to do so for their protection. Payment forms will be collected and stored separately from data in a locked cabinet for up to 6 years.

After participation, RedCAP data will be downloaded in excel format to the secure MUSC server. Finally, physiology data files will also be linked only to participant code; these data will be transferred to an MUSC Box account that is only linked to the participant’s code.

In terms of publication, data will be published in aggregate form, so individual participants will not be identifiable in the final manuscript. No identifying information will be published.

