15.0 Risks to Subjects

Physiology: The study procedures may involve non-invasive recording of EMG and ECG, so the risk with this is minimal. For external sensors used for ECG and EMG, adhesive disks are used. Removal of these adhesives may result in mild local irritation or redness.

Ear Stimulation: Ear stimulation is safe, however there are some risks associated with stimulating the ear: There may be local discomfort. This will likely be temporary. In extreme cases burns might occur. We will video monitor any potential burns and will stop stimulation and advise subjects to apply vitamin E cream. Tissue surrounding the ear may be sensitive, sore or feel slight numbness. Hopefully this will be temporary and will go away after stimulation is turned off.

Potential Headache, Dizziness, and Facial Pain: Ear stimulation might cause headaches or face pain, which should resolve shortly after treatment.

Safety in case of pregnancy: This protocol will exclude pregnant women. The risks of using taVNS with pregnant women are currently unknown. If in the screening and consent a patient is a woman of childbearing age, a urine pregnancy test will be completed.

Cold Pressor Test: Prior studies have shown the safety and feasibility of the cold pressor test in neurotypical populations. Subject's discomfort will be monitored closely and throughout the test. Previous studies have shown that neurotypical participants are able to tolerate and complete the cold pressor test without residual discomfort following the test. Subjects will have the option to withdraw at any time throughout the test if discomfort is too great or per their preference. Of note, active taVNS is hypothesized to attenuate the sympathetic response to the cold pressor test. Thus, one out of the two cold pressor tests may have a higher risk of discomfort (subjects will receive active and sham taVNS in randomized order).

Risk of Increased/Decreased Heart Rate: The Cold Pressor Test is associated with an acutely elevated heart rate. Other studies have shown the safety and feasibility of this technique, and elevations in heart rate have been shown to stay within the normal range of physiologic functioning. taVNS is also associated with decreases in heart rate. The safety and feasibility of taVNS has also been shown by prior studies. Study staff will closely monitor changes in heart rate, as well as patient's comfort levels, and will respond to changes accordingly.

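### Section 3.0 tells the whole research team the stimulation condition, with no exception for those who score the recordings and no stated safeguard against cueing the self-ratings

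*Protocol*

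**What the plan says.** Section 3.0 holds the protocol's one statement on blinding: "Subjects will be blinded to stimulation condition, but the research team will know whether patients are receiving active or sham stimulation". It names the team as a whole and exempts nobody.

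On the primary outcome, Section 4.0 has heart rate, HRV and blood pressure recorded continuously by Biopac equipment. Section 12.0 then says: "The psychophysiological data will be processed using standard protocols which have previously been used in this lab and in various other studies". It adds that "physiology data files will also be linked only to participant code". It does not say who does the processing, or whether that person knows the condition.

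On the secondary outcome, Section 4.0 specifies visual analog scales for pain, stress and anxiety. Section 10.0 places ratings in the resting period before the cold pressor test, during immersion ("During the exposure to the ice water, subjects will again rate subjective anxiety, stress, and pain") and in the resting period afterwards. The stimulation overlaps the test: "stimulation will start prior to CPT and continue throughout the duration of the CPT".

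On who is in the room, Section 7.0 describes a COVID-19 precaution of "limiting use of space to no more than the participant and the study researcher". Two further provisions require contact about discomfort at the same time. Section 10.0 says "Participants will be assessed during stimulation for discomfort or adverse events over the course of stimulation", and Section 15.0 says that the subject's "discomfort will be monitored closely and throughout the test".

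**The concern.** Section 1.0 states directional hypotheses: a smaller sympathetic response and lower pain and stress ratings under active stimulation, and an anxiolytic effect. When staff know both the condition and the expected direction, bias can enter at two steps even though the subject is blinded.

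- **Scoring.** Turning a continuous recording into analysable values involves judgement about artefacts and about where the analysis windows begin and end. Someone who knows the condition could make those judgements differently under active and sham stimulation without meaning to.
- **Ratings.** A researcher who knows the condition may ask about discomfort, or prompt a rating, in a different manner in the two periods. Blinding the subject does not close this route, because the cue would come from the researcher.

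Aim 2 rests on the ratings, as does Aim 3 so far as it uses them. Aim 1 rests on the physiological signals, which are less exposed.

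**Working it through.** The protocol gives no figure on blinding, so there is none to reproduce and no arithmetic to run. The check is a reading of the sections against each other.

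1. **Who knows the condition?** Section 3.0 says the research team. The wording is affirmative and general. No other section narrows it or sets apart those who process or analyse data.

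2. **Does the participant code mask the condition?** Sections 10.0, 12.0 and 15.0 present the code as protection of confidentiality. A code that replaces a name does not hide which of a subject's two periods was active. Nothing says that files carry a masked condition or period label. The code cannot be counted as blinding.

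3. **Where can awareness affect the primary signals?** Recording is continuous and by instrument (Section 4.0), so acquisition leaves little room for staff judgement. What remains is mainly the processing in Section 12.0, that is, artefact handling and window choice. That section refers to standard laboratory procedures and published guidelines. These may well fix the rules, but the protocol does not say that they mask the person applying them.

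4. **Is the researcher present at the ratings aware?** Section 7.0 allows no more than the participant and the study researcher in the space. Section 3.0 says the research team knows the condition. Together they make it probable that the person present knows. This is an inference from two sections, and no single sentence states it.

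5. **Are the ratings protected in some other way?** Section 4.0 names visual analog scales. The confidentiality paragraphs of Sections 10.0 and 15.0 describe self-report data in Likert format. Section 12.0 stores the ratings in REDCap. None of these says how the subject is prompted or who enters the mark. Self-entry after a fixed prompt may already be the practice, but the text does not show it.

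6. **Which ratings are exposed?** Ratings before, during and after immersion may all be given in the same researcher's presence. Those in the ice water coincide with stimulation and with the required checks on discomfort, but they are not the only ones affected.

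7. **How large is the effect?** The document has nothing from which to estimate it. Counting ratings or recordings would describe how much data is exposed, not how far any of it is biased.

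**The case against.** The strongest case on the other side is that the protocol declares a single-blind design openly and contradicts nothing. Scoring rules and masked processing are commonly left to an analysis plan or laboratory procedure. The Section 3.0 sentence stands among text on device use and can be read as awareness while stimulation is delivered. The ratings come from blinded subjects, the primary signals come from equipment, and the study is a pilot.

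Much of this stands. The absence of scoring rules from the protocol is not a fault. What remains is that Section 3.0 makes a positive statement about the whole team. An analysis plan that kept scorers masked would depart from that statement as written, so the protocol sentence is the right place for the correction.

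A reader might infer more than the text supports:

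- **That an aware researcher is known to collect the ratings.** Section 7.0 sets a maximum occupancy as an infection precaution and does not assign the task of collecting ratings. Awareness is probable, not stated.
- **That staff score or interpret the ratings.** No section says so. The route is unintended cueing, which is plausible but not shown.
- **That the primary result is compromised.** Continuous instrument recording limits the exposure mainly to the scoring step.
- **That time in the water is biased in a particular direction.** Immersion is for up to three minutes and staff may end participation for distress, but nothing in the document gives the direction of any such effect.

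**Conclusion.** The point holds as a cheap improvement of minor to moderate weight. It is not an error or an internal contradiction. Section 3.0 makes the whole team aware of the condition, no section exempts those who process the recordings, and participant codes do not supply the missing masking. The self-ratings are the more exposed outcome, through cueing. The primary signals are exposed to a lesser degree, mainly through artefact handling and window choice. The size and even the presence of bias cannot be established from the document.

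The conclusion rests on two readings: that the research team in Section 3.0 includes those who later process the files, and that the researcher allowed in the room under Section 7.0 is one of that team. Both are natural readings, but neither is spelled out. If scoring is already masked and subjects already enter their own ratings after a fixed prompt, stating this in the protocol settles the matter.

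**What to change.** Three changes of wording:

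- **Section 3.0:** limit knowledge of the condition to the session operator and anyone who needs it for safety.
- **Section 12.0:** have existing team members without the key clean and score the heart rate, HRV and blood pressure recordings under coded condition labels, by rules fixed beforehand. The rules themselves may sit in an analysis plan.
- **Section 10.0:** have subjects enter the visual analog scales themselves after a scripted prompt that is identical in both periods.

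Leave the safety monitoring and withdrawal provisions as they are.

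The cost is the wording, a short script, and coded labels for two period recordings per subject. With the figures in Section 6.0 that is 14 × 2 = 28 recordings at the minimum number of completers and 24 × 2 = 48 if everyone recruited completes. This is workload, not a measure of bias. No extra person or procedure is added in the room. At least one existing team member must be kept without the key. Section 13.0 mentions a PI, co-investigators and study personnel, but the team size is not given, so this needs confirming. The operator remains unblinded, so the bias is reduced and not removed.
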